### B) Before and after intervention: Blood test Analysis and Anthropometric measurements

#### 1. Lipid profile, Anthropometric measurements

Parameter	Before dietary intervention	After dietary intervention
Total cholesterol (mmol/l)		
LDL-cholesterol (mmol/l)		
HDL-cholesterol (mmol/l)		
Triglycerides (mmol/l)		
Blood pressure (mmHg)		/
Body weight (kg)		
Body waist (cm)		

## 2. Oral glucose tolerance test (OGTT)

Sampling time after glucose consumption (min)	Before dietary intervention		After dietary intervention	
	Glucose level (mmol/l)	Insulin level (μU/ml)	Glucose level (mmol/l)	Insulin level (μU/ml)
0				
30				
60				
120				

## 3. Gut microbiota analysis and short chain fatty acids measurements

Faecal samples will be obtained before and after dietary intervention.

Analysis of gut microbiota composition will be performed followed DNA extraction, with several methodologies; Denaturing Gradient Gel Electrophoresis (DGGE), qPCR, new generation sequencing (illumine Miseq platform).

### Short-chain fatty acids determination

Short-chain fatty acid	Before dietary intervention (g/kg)	After dietary intervention (g/kg)
Butyric acid		
Acetic acid		
Propionic acid		

#### 4. 72-hour dietary recall

Dietary recall will be performed three times before and during dietary intervention to obtain average nutrient intake:

Average nutrition intake per 100 g	Before dietary intervention	Between dietary intervention
Energy (kcal)		
Protein (g)		
Fat (g)		
Total carbohydrates (g)		
Total dietary fibre (g)		
Water (g)

## 1. INTRODUCTION

This document is established to provide information about dietary clinical trial "Impact of Consumption of Beta-glucans on the Intestinal Microbiota and Glucose and Lipid Metabolism". Document was prepared when clinical trial was completed and contains basic information about study design, protocol and methodology used.

### 1.1. Objective

The purpose of this study was to investigate if daily consumption of barley beta-glucans effect lipid and glucose metabolism and alter intestinal microbiota composition in participants with metabolic syndrome or with high risk for metabolic syndrome development. We conducted 4-week long, placebo controlled dietary study, where participants consumed bread with (test group) or without (control group) enriched beta-glucans bread.

### 1.2. Hypothesis

1. 4- week consumption of beta-glucans alters the composition of intestinal microbiota and changes the ratio of different bacteria groups and consequently effects production of short chain fatty acids in a population with metabolic syndrome or with high risk for metabolic syndrome development.
2. 4- week consumption of beta-glucans has an influence on glucose metabolism and consequently improves insulin resistance within people with metabolic syndrome or with high risk for metabolic syndrome development.
3. 4 - week consumption of beta-glucans improves specific plasma lipid content in a population with metabolic syndrome or with high risk for metabolic syndrome development.

## 2. STUDY METHODS

### 2.1. Trial design and participants enrolment

[figure not shown]
Study was performed as double blind, randomised, placebo controlled clinical trial and was performed regarding to CONSORT 2010 recommendations for randomised clinical trials [1]. The study was approved by the Republic of Slovenia National Medical Ethics Committee (112/08/13). Participant enrolment was performed within a national programme for metabolic disorder prevention in community health centres in Slovenia in association with family medicine doctors. Participants that met including criteria and had metabolic syndrome or high risk for metabolic development were suggested to participate in clinical trial.

Table 1: **INCLUSION CRITERIA**

Parameter	Inclusion criteria*
Age	30 – 70 years
Total cholesterol levels	$\geq 5.0 \text{ mmol/L}$
Waist circumference	Women $> 80 \text{ cm}$ Men $> 94 \text{ cm}$
And presence of at least one of the remaining determinants for MS	
HDL-cholesterol	Women $< 1.29 \text{ mmol/L}$ Men $< 1.03 \text{ mmol/L}$
Raised blood pressure	Systolic blood pressure $\geq 130 \text{ mm Hg}$ Diastolic blood pressure $\geq 85 \text{ mm Hg}$
Raised fasting plasma glucose	$\geq 5.6 \text{ mmol/L}$

\*Participants diagnosed with metabolic syndrome and meeting the age criteria were directly included in the study. Exclusion criteria were diabetes type II, thyroid disorders, kidney disorders and antibiotic treatment.

Participants who met the inclusion criteria started the intervention after agreement with study conditions and procedures. Participants that agreed to participate were randomised and enrolled in trial as the control or test group (Figure 1).

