## **STUDY PROTOCOL**

### **»Impact of Consumption of Beta-glucans on the Intestinal Microbiota and Glucose and Lipid Metabolism«**

#### **Introduction**

Metabolic syndrome (MS) is a complex lifestyle disease manifesting metabolic disorders such as abdominal obesity, dyslipidemia, hyperglycemia and hypertension. There are many studies reporting how gut microbiota correlates with metabolic disorders or contributes to the development of obesity through increased energy harvest. An increasing interest in finding the diet that could regulate the composition of gut microbiota and consequently improve the individual conditions related to some of the metabolic disorders, exists. The aim of our study will be to investigate, whether consumption of barley beta glucans can positively modulate the composition of gut microbiota and metabolic parameters related to MS. Barley beta glucans are polysaccharides found in kernel endosperm and improve both lipid and glucose metabolism. The effects of barley beta glucans on gut microbiota composition are still poorly investigated in human clinical trials.

We will perform a double-blind, placebo controlled, randomized clinical trial with volunteers diagnosed with MS. The exact study protocol and procedure will be explained to the participants, who will meet inclusion criteria. After assignment of participation agreement, participant will be randomized and allocated to test or placebo group. Before and after the dietary intervention, anthropometric measurements, blood analysis, including oral glucose tolerance testing (OGTT), and fecal sampling will be performed. Participants will daily complete food frequency questionnaire and detailed 72-hour dietary recall. During intervention participants will daily consume test bread with added 6g beta glucans or bread without added beta-glucans.

The study was approved by the Republic of Slovenia National Medical Ethics Committee (112/08/13).

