## Study protocol

### A) Participants information and inclusion criteria

Name	
Surname	
Age	
Body height & body weight (cm, kg)	
Diabetes type 2	
Kidney dysfunction	
Thyroid dysfunction	
Treatment for hypercholesterolemia (not hypertension)	
Total cholesterol (mmol /l)	
Body Mass Index (BMI)	

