## 3. STATISTICS

For analysis of participants' anthropometric and metabolic characteristics, RT-PCR results and microbial richness and diversity measures, a Wilcoxon signed-rank test or paired samples *t*-test were used as appropriate with  $P < 0.05$  for significance and  $P < 0.1$  for reporting a trend (SPSS v.21). Statistical sequence analysis was based on differential abundance testing using the 'R' package DESeq 2 [16]. Differential abundance that occurred in test group subjects after dietary intervention but not in the control group was determined in a model with interaction (time, group and subject). Significance was reported for  $P < 0.05$  after multiple inference correction (Benjamini-Hochberg), and all OTUs with  $P < 0.05$  before correction were screened for trends. Initial microbial abundance differences between test group subjects who responded to dietary intervention with a 10 % plasma total cholesterol concentration drop and those without reduction were also tested with Deseq2 [16]. OTUs with  $P < 0.1$  after correction were considered significant. Alpha and beta diversity measures and PCoA of weighted UniFrac distances were calculated and plotted with Phyloseq [15].

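### The SAP admits people on cholesterol treatment, and direct entrants with metabolic syndrome below 5.0 mmol/L, without excluding or adjusting for them, and its lipid tests do not compare the arms

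*SAP*

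**What the plan says.** Protocol part A, headed "Participants information and inclusion criteria", is a blank form. Beside type 2 diabetes, kidney dysfunction and thyroid dysfunction it lists "Treatment for hypercholesterolemia (not hypertension"), and below these "Total cholesterol (mmol /l"). It gives no cholesterol threshold and does not say what a positive answer on treatment means for entry. The protocol Introduction describes a "randomized clinical trial with volunteers diagnosed with MS".

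SAP section 2.1, Table 1, sets a floor of 5.0 mmol/L in the row "Total cholesterol levels". The footnote opens a second route: "Participants diagnosed with metabolic syndrome and meeting the age criteria were directly included in the study". It continues: "Exclusion criteria were diabetes type II, thyroid disorders, kidney disorders and antibiotic treatment". Cholesterol treatment is not on that list and appears nowhere else in the SAP.

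For metabolic measures, SAP section 3 names a Wilcoxon signed-rank test or a paired t-test. It also plans a microbial comparison, within the test group, between subjects who "responded to dietary intervention with a 10 % plasma total cholesterol concentration drop and those without reduction".

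**The concern.** Hypothesis 3 (SAP section 1.2) asks whether beta-glucans improve plasma lipids. Table 1 selects people with raised total cholesterol, but the selection does not reach direct entrants, and nothing in the SAP keeps out treated people by either route. Three of the four clinical-status items on the protocol form became SAP exclusions and the fourth, cholesterol treatment, disappeared. A reader cannot tell whether treated people could enter.

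If such people took part and have less room to improve, the average lipid effect is smaller and the responses more mixed. The planned tests would not show this, since they use neither treatment nor a between-arm contrast. The 10% responder split is exposed in the same way, because it takes no account of baseline cholesterol or treatment.

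**Working it through.** **1. The sections side by side**

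| Item | Protocol part A | SAP section 2.1 | SAP section 3 |
|---|---|---|---|
| Type 2 diabetes, kidney, thyroid | recorded | exclusions | not used |
| Cholesterol treatment | recorded, no direction | not mentioned | not mentioned |
| Total cholesterol | recorded, no threshold | at least 5.0 mmol/L by the Table 1 route; not required for direct entry | tested before against after; also defines the 10% split |

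**2. Whom the threshold binds.** Direct entry needs a diagnosis of metabolic syndrome, age 30 to 70 and none of the listed exclusions. If every volunteer had the diagnosis, as the protocol Introduction says, the threshold would bind nobody. Under the wider population of SAP section 1.1 it binds only the high-risk group.

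**3. What the lipid tests do.** A paired test on before and after values works within one arm. The only analysis in SAP section 3 that contrasts the arms is the sequencing model with a time-by-group interaction. For lipids, no test-versus-control comparison, baseline adjustment or treatment covariate is stated.

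**4. Size, by assumption.** The documents give no sample size, effect, standard deviation, power, treated count or count of direct entrants, so there is no figure to reproduce. Let f be the affected share and k their response as a fraction of the full effect. The mean effect is multiplied by m = (1 − f) + f × k. With a two-sided 5% level and an assumed 80% power at full effect, power = Φ[(1.960 + 0.842) × m − 1.960], and the required sample size is multiplied by 1/m².

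| f | m (k = 0.5) | Power | Sample size factor | m (k = 0) | Power | Sample size factor |
|---|---|---|---|---|---|---|
| 10% | 0.95 | 76% | 1.11 | 0.90 | 71% | 1.23 |
| 20% | 0.90 | 71% | 1.23 | 0.80 | 61% | 1.56 |
| 30% | 0.85 | 66% | 1.38 | 0.70 | 50% | 2.04 |
| 40% | 0.80 | 61% | 1.56 | 0.60 | 39% | 2.78 |

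At f = 30% and k = 0.5, m = 0.70 + 0.15 = 0.85, a loss of 15%.

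**5. Would restricting the analysis help?** Take only untreated participants at or above 5.0 mmol/L, with the same standard deviation. The effect rises by 1/m and the standard error by 1/√(1 − f), so signal-to-noise relative to the full set is √(1 − f)/m. At k = 0.5:
- f = 10%: 0.949/0.95 = 0.999
- f = 30%: 0.837/0.85 = 0.984
- f = 40%: 0.775/0.80 = 0.968

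Restriction gains nothing at half response. At f = 30% it gains only if m < 0.837, that is, if k is below (0.837 − 0.70)/0.30 = 0.46.

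**The case against.** The strongest reply has three parts.

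- The protocol form is blank and gives no direction. Cholesterol treatment sits among items that were exclusions, so treated people may have been screened out and the item simply left off the SAP list. This stands: the documents show what is permitted, not who was enrolled.
- Hypothesis 3 concerns people with metabolic syndrome or at high risk of it, not people with raised cholesterol, and the outcomes include HDL-cholesterol and triglycerides (SAP section 2.3). Direct entry fits that population. This also stands, so the eligibility rule does not contradict the objective.
- Randomisation and blinding mean that treated or low-cholesterol participants are not expected to favour one arm. That is correct for a between-arm comparison, but the SAP plans none for lipids.

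A reader might go further and infer that the lipid objective was in fact tested partly in people with normal or drug-controlled cholesterol. No baseline values or counts support that.

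A reader might also infer that drugs started or changed during the four weeks created false responders. The documents mention no such change. Someone who starts a drug during the trial was untreated at entry, so an entry rule on treatment would not have prevented it. Nor does the responder split necessarily cover the whole test arm. Only 14 test-group participants were sequenced (SAP section 2.3.4), and on the wording of section 3 a fall of less than 10% belongs to neither group.

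**Conclusion.** The point holds in a limited form. The SAP permits participants on cholesterol treatment, and direct entrants below 5.0 mmol/L within the age range and listed exclusions. It neither excludes nor adjusts for them, although the protocol form records both items. The consequence is possible dilution and extra variability in the lipid results, which the within-arm tests cannot address.

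The size cannot be determined from the documents. The 15% loss rests on an assumed 30% share, an assumed half response and an unchanged standard deviation; the share and the response have no source in the documents. If no one affected was enrolled, the loss is zero. The lack of a between-arm lipid comparison does not depend on any of these assumptions.

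**What to change.** For each lipid outcome, make the main analysis a test-versus-control comparison of the post-intervention value in all participants, adjusted for the baseline value. If any treated people were enrolled, also adjust for the treatment item in protocol part A. Baseline and final lipids have fields in protocol part B.1, so if the forms were completed this costs SAP wording and one model per lipid. The adjustment removes variation linked to baseline and treatment and gives an estimate of the difference between arms. It does not undo dilution: the estimate remains an average over the mixed population.

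Reconcile protocol part A with SAP section 2.1 on whether treated people could enter. If they could not, one sentence settles that part and the treatment covariate is unnecessary. Report by arm the numbers treated, below 5.0 mmol/L and directly entered. The form has no field for a diagnosis of metabolic syndrome, so the last count depends on enrolment records.

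Label any analysis restricted to untreated participants at or above 5.0 mmol/L as a post hoc sensitivity analysis, since the SAP was written after the trial ended (SAP section 1), and accept its wider interval. Changes of treatment during the trial cannot be handled by a new question or by removing participants: the trial is complete and the forms have no field for such changes.

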**Figure 1: Participants flow diagram.**

## 2.2. Dietary intervention

Participants consumed bread with beta-glucans content of approximately 3,4 g beta-glucans per 100 g of bread in 4-week long intervention. Before study participants had two-week washout period without consuming any pre- and pro-biotics. Participants retained their usual eating habits during the

intervention. A 72-hour dietary recall was performed in order to control participants' diet and eating habits. Participants were told to consume 200 g of bread daily, not knowing whether the bread was experimental or control. Participants included in the test group consumed 200 g of BGB, containing more than 6 g of barley beta glucans, daily. Participants in the control group consumed 200 g of CWB without added beta glucans. 72-hour dietary recall was performed before intervention and at the end of the trial to evaluate daily nutrient and energetic input of each participant.

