#### 2.3.3. Faecal sampling and DNA isolation

Faecal samples were collected one day before the start and at the end of the intervention. The samples were frozen immediately and stored at -20 °C until use. DNA was isolated within one week after sampling. DNA isolation was performed in parallel using the protocol for isolation of DNA from faecal samples described by Yu and Morrison (2004) [9].

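### The pre-/probiotic restriction is stated only for the two weeks before baseline, so the two stool samples are taken under different stated conditions, and the within-arm paired tests cannot separate resumed use from an effect of the bread

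*SAP*

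**What the plan says.** SAP section 2.2 contains the only restriction on these products: "Before study participants had two-week washout period without consuming any pre- and pro-biotics". It then gives the rule for the bread period: "Participants retained their usual eating habits during the" intervention. SAP section 2.3.3 fixes the sampling: "Faecal samples were collected one day before the start and at the end of the intervention". The first sample thus falls at the end of the washout and the second after four weeks for which no such restriction is stated. The protocol does not mention the washout.

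Habitual pre-/probiotic use is not a reason for exclusion. SAP section 2.1 says: "Exclusion criteria were diabetes type II, thyroid disorders, kidney disorders and antibiotic treatment". Antibiotics are listed there without a time window.

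On monitoring, the protocol's Introduction says: "Participants will daily complete food frequency questionnaire and detailed 72-hour dietary recall". The SAP does not mention the questionnaire and describes the recall as follows: "72-hour dietary recall was performed before intervention and at the end of the trial to evaluate daily nutrient and energetic input of each participant". The protocol's recall table (part B, item 4) has rows for energy, protein, fat, carbohydrate, fibre and water only.

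On analysis, SAP section 3 (Statistics) specifies for "RT-PCR results and microbial richness and diversity measures, a Wilcoxon signed-rank test or paired samples" *t*-test, at P<0.05 for significance and P<0.1 for a trend. It names no between-arm contrast for these measures. OTU abundance alone is tested against the control arm, in a DESeq2 model with time, group and subject.

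**The concern.** A washout is meant to put the samples being compared on the same footing. If it covers only the first of two samples, it can create a difference that would not exist without it. A habitual user stops for two weeks, gives the baseline sample, may go back to the product, and gives the final sample while using it. That person's before-after change then contains a component unrelated to beta-glucans.

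Microbiota composition and the resulting short-chain fatty acid production are the SAP's first hypothesis. A paired test within one arm has no means of separating this component from an effect of the bread. A course of antibiotics between the two samples would raise the same difficulty, and the documents do not say that one would be recorded.

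**Working it through.** The documents give no sample size calculation, power or effect size, so there is no planned figure to reproduce. The first step compares the stated conditions. The second shows how large the effect could be under stated assumptions.

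**Step 1: conditions at the two samples**

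| | Baseline stool sample | Final stool sample |
|---|---|---|
| Timing (SAP 2.3.3) | one day before start | end of week 4 |
| Pre-/probiotic rule (SAP 2.2) | two weeks without | none stated |
| Diet rule (SAP 2.2) | washout | usual habits |
| Item recording these products | none described | none described |

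**Step 2: inputs for the illustration**

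- From SAP section 2.3.4: 14 test and 9 control participants sequenced, and 2 × (14 + 9) = 46 samples, which agrees with the stated 46. The number with RT-PCR results is not given; a larger number would raise the paired-test rates below.
- Assumed: a share f of participants are habitual users who all resume, with f = 10%, 20% or 30% in both arms.
- Assumed: resumption shifts the measure by d = 1 SD of the before-after change, always in the same direction.
- Assumed: normal changes, two-sided tests and no effect of the bread.

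**Step 3: formulas**

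- Mean spurious change in each arm: f × d.
- Variance of change: 1 + d² f(1 − f).
- Approximate non-centrality of the paired *t*-test: f d √14 / √(1 + d² f(1 − f)).
- Expected between-arm difference in change: f d − f d = 0.

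For f = 20%, the non-centrality is 0.2 × 3.742 / √1.16 = 0.69. For f = 30%, it is 0.3 × 3.742 / √1.21 = 1.02.

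**Step 4: simulated rejection rates (40,000 runs, d = 1 SD)**

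| Share of users | Paired test, n=14, P<0.05 | Paired test, P<0.1 | Between-arm *t*-test of change, 14 v 9, P<0.05 | Significant in test arm, not in control |
|---|---|---|---|---|
| 0% | 0.049 | 0.099 | 0.050 | 0.046 |
| 10% | 0.061 | 0.119 | 0.048 | 0.058 |
| 20% | 0.096 | 0.170 | 0.049 | 0.089 |
| 30% | 0.154 | 0.249 | 0.048 | 0.138 |

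The result depends strongly on the assumptions. At 30% users, a shift of 0.5 SD gives 0.079 for the paired test at P<0.05, and a shift of 1.5 SD gives 0.236. The between-arm test stays at its nominal level throughout.

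**Step 5: cost of excluding users**

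Keeping everyone inflates the variance of the between-arm difference by 1 + f(1 − f): 1.16 at 20% users and 1.21 at 30%. Excluding users inflates it by about 1/(1 − f): 1.25 and 1.43. With an assumed bread effect of 1.2 SD, simulated between-arm power at 20% and 30% users is about 0.70 and 0.68 keeping everyone, against about 0.65 and 0.58 after exclusion.

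**The case against.** The strongest objection is that silence is not permission. The SAP was written after completion and describes itself as basic information. It says that participants agreed to study conditions that are not reproduced, and consent pages are not part of the public text. The restriction may have continued in practice. This stands as far as it goes: the documents do not show that anyone resumed. But the stated rule for the bread period is to keep usual habits, with no exception for these products, so the text as written leaves resumption open.

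A reader might also infer that an uneven split of users between 14 and 9 people biases the DESeq2 comparison. The documents do not support that. The trial is described as randomised and double blind, so chance imbalance in an unmeasured factor is already allowed for in the type I error of a valid between-arm test. A gap of 20 percentage points or more in the share of users has probability 0.24 at 20% users and 0.31 at 30%, yet the simulated between-arm error rate stays near 0.05. The cost there is added noise. The check used a *t*-test on normal changes, not DESeq2 itself, but the reasoning from randomisation is the same.

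Finally, it can be said that the real weakness is the reliance on within-arm tests, which credit any common time effect to the bread. That is largely right, and it shapes the remedy. The one-sided washout still deserves its own mention, because it is a source of such an effect that the design itself introduces and could have avoided.

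**Conclusion.** The point holds as a gap in the design as written. The pre-/probiotic restriction applies to the baseline stool sample and is not stated for the final one, and the paired tests of RT-PCR, richness and diversity would attribute any resulting shift to the assigned bread. The OTU interaction model is exposed only to extra noise. For short-chain fatty acids, SAP section 3 names no analysis, so the exposure there cannot be judged.

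The size is unknown. The rates of about 6%, 10% and 15% at P<0.05 rest on 10%, 20% and 30% users who all resume, a 1 SD shift in one direction and 14 people. None of these assumptions about users or shift comes from the documents, and with few users the rate is close to nominal.

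A reader might conclude that the reported microbiota changes are artefacts, or that a false beta-glucan effect has been shown. Neither follows. The documents do not say whether resumption occurred, and a shift shared by both arms is not a difference between breads. For antibiotics, the text leaves open whether the exclusion applied at entry only; it does not show that courses during the study were ignored.

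**What to change.** **In the design text, and for any repeat study.** State that the pre-/probiotic restriction runs from the start of the washout until the final stool sample in both arms, and that usual eating habits apply to everything else. Record any pre-/probiotic or antibiotic use between the two samples, by arm. The cost is one sentence in the participant instructions and two items on a form. The small downside is four more weeks without such products for habitual users.

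**In the analysis.** Base RT-PCR, richness and diversity conclusions on the between-arm difference in change, with paired within-arm results as description only. This needs no new data and removes any shift common to both arms, whatever its source.

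**For the completed trial.** State whether the restriction in fact continued to the final sample, and report any recorded exposure by arm. The protocol's daily questionnaire may hold this, but no section says that it captured these products. If exposed participants can be identified, exclude them only in a sensitivity analysis, noting the loss of power and that selection on behaviour after randomisation can itself distort the comparison. If no record exists, state the limitation.
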